- 1. Aged 18-65
- 2. Male or female age 18-65 years
- 3. BMI 18.5-45 kg/m² based upon self-reported height and weight
- 4. Have an iPhone and an operable Apple ID, password, and email address and is willing to use these to collect data during the study, acknowledging that data usage, and associated charges, are a result of study participation

Exclusion Criteria are:

- 1. For females, pregnancy or breast feeding
- 2. Currently diagnosed with an eating disorder
- 3. Disease that severely affects metabolism, including diabetes, hypercholesterolemia, or dyslipidemia.
- 4. Has gained or lost more than 10 lbs in last 3 months
- 5. PBRC Faculty/Staff Member
- 6. Has suffered serious mental illness that has resulted in serious functional impairment and has substantially interfered with one's life activities within the last 5 years.
- 7. Any other medical, psychiatric, or behavioral factors in the judgement of the Principle Investigator or Medical Investigator that may interfere with study participation or the ability to follow the protocol

Number of Subjects

We expect up to 15 participants to complete both Phase 1 and Phase 2. Pennington Biomedical Research Center employees are not eligible to participate.

Page 2 of 8 Version 3: 8/6/2020

Recruitment Methods

A sample of up to 15 adults will be recruited from the Baton Rouge, Louisiana area to participate in both Phase 1 and Phase 2.

Study Timelines

Participants will complete the procedures as noted in the Procedures section. The study involves one visit to Louisiana State University (LSU) campus or the Pennington Biomedical (PBRC) campus for Phase 1. Phase 2 will be completed in-person or remotely after Phase 1 before participants make a return visit to either LSU or PBRC afterwards.

It will take up to six months to recruit participants and have them complete Phase 1 and Phase 2. All data analyses and study cessation will occur shortly after.

Study Endpoints

The primary endpoint of this study is validity and reliability of portion size and energy intake measurement, measured with the PortionSize app in controlled and free-living conditions.

Secondary endpoints include satisfaction with the PortionSize app and the ease of using the app.

Procedures Involved

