Phase 1: Testing the PortionSize Smartphone App. The validity, reliability and satisfaction of the PortionSize app under controlled conditions will be quantified in the Phase 1. Participants will partake in an in-person lab visit at either LSU or PBRC. All assessments will be conducted in a controlled room. Initially, participants will complete an informed consent. Then participants will have their height and weight recorded and will complete a set of questionnaires on demographics and lifestyle factors. A food frequency questionnaire (Diet History Questionnaire, Version 3.0 [5]) will also be administered. Afterwards, participants will be trained on using the PortionSize app.

Next, participants will use the app to measure the portions, energy composition and the food groups of pre-weighed foods that differ in size and composition. These food items will be provided by the researchers and will serve as the criterion measures of portion size, energy content and food group quantity, further to rater analysis of food photos [6]. Food portions administered will be carefully selected to reflect a plethora of food items and portion sizes. Some selected food items will be reassessed within and between users to obtain intra- and inter-rater reliability, respectively. The participant will not consume the food items they are administered to assess.

Participants will complete a user preference survey (Appendix 1: PortionSize User Preference Survey (Phase 1)) to report their satisfaction with the PortionSize app. This survey evaluates how much participants liked the app and includes questions about ease of use and satisfaction. The survey was modeled from surveys developed to assess satisfaction with the Remote Food Photography Method app [6]. Afterwards, the participants will complete the Computer System Usability Survey (CSUQ) [7].

Page 3 of 8 Version 3: 8/6/2020

Phase 2: Testing the PortionSize Smartphone App in free-living conditions

Phase 2 will occur in participants' natural environment and will involve the 15 participants from Phase 1. In free-living conditions, participants will capture before and after pictures of the foods and food supplements they consume and use the app to quantify the portion sizes of the items within the pictures. Participants will use the app for 3 days (two weekdays and one weekend day) in free-living conditions.

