At the end of Phase 2, we will compare the portion size, energy/macronutrient composition and food group data collected from PortionSize and compare these to rater analysis of food photos. Participants will also return to complete the same CSUQ survey on app usability. Lastly, the PortionSize User Satisfaction Survey (Phase 2) (Appendix 2) will be administered to assess participant satisfaction and the ease of using PortionSize app for capturing information about portion sizes.

Description	Phase 1	Phase 2
Consent and eligibility	x	
Remote training on the use of app to capture food images and quantify portion sizes	X	
Lifestyle and Demographics Questionnaire, RFPM Lifestyle Interview, Food Frequency Questionnaire, body weight, height, BMI	X	
Use of app to measure pre-weighed lab meal portions	X	
Pen and paper User Satisfaction Surveys	х	
Instructed to use app over 3-day period in free-living setting		х
Return for pen and paper User Surveys		x

All named personnel have experience with the IRB approval process and field experiment designs.

Data and Specimen Management

Analysis

Phase 1 analysis objectives include:

- 1) Determining if portion size estimation measured with the PortionSize app is significantly different from criterion values (directly weighed food portions).
- 2) Determining if energy, macronutrient, saturated fat, added sugar and food group estimation measured with the PortionSize app is significantly different from criterion values (directly weighed food portions and rater analysis of food photos).
- 3) Determining how reliable the PortionSize app is in examining energy, macronutrient, saturated fat, added sugar and food group values.
- 4) Determining the differences in energy, macronutrient, saturated fat, added sugar and food group values between rater analysis of the food photos and directly weighed foods.
- 5) Determining the differences in estimated energy, macronutrient, saturated fat, added sugar and food group error between the PortionSize app and the rater analysis of food photos.
- 6) Determining if the PortionSize app provides a reliable measure of portion size, energy intake, macronutrient intake, saturated fat, added sugar and food groups.
- 7) Determining if participants are satisfied with the PortionSize app as measured in Appendix 1 (PortionSize User Preference Survey (Phase 1)).
- 8) Determining if the PortionSize app is easy to use and provides adequate instructions for use.

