- 9) Qualitative assessments by respondents of the desirable and undesirable features of the app.

Phase 2 analysis objectives include:

- 1) Determining if portion size estimation measured with the PortionSize app in free-living conditions is significantly different from the criterion value (rater analysis of food photos).
- 2) Determining energy, macronutrient, saturated fat, added sugar and food group estimation measured with the PortionSize app in free-living conditions is significantly different from the criterion value (rater analysis of individual food photos).
- 3) Determining if energy intake estimation measured with the PortionSize app in free-living conditions is significantly different from estimated energy requirements [8-10].
- 4) Determining if energy intake estimation measured from the rater analysis of food photos is significantly different from estimated energy requirements [8-10].
- 5) Quantifying satisfaction levels with the PortionSize app as measured in Appendix 2 (PortionSize User Preference Survey (Phase 2)).
- 6) Qualitative assessments by respondents of the desirable and undesirable features of the app.

Withdrawal of Subjects

Subjects may be withdrawn from the study if they are non-compliant with study procedures and they will be notified of their withdrawal via telephone or mail.

Subjects may voluntarily withdraw from the study at any time. No additional data will be collected and they will be considered drop outs in the study.

Page 5 of 8 Version 3: 8/6/2020

Risks to Subjects

This study involves no greater than minimal risk. The main risk is breach of confidentiality, and the PBRC team will work to minimize this during data collection, handling, and analysis.

Potential Benefits to Subjects

Participants may benefit by increased awareness of their portion sizes with various food groups.

Setting

All research procedures will be conducted at LSU main campus, PBRC's campus, or remotely through videoconference calling, and in participants' natural environment.

Resources Available

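### Do the Phase 2 comparisons with estimated energy requirements need an exploratory label because energy balance and recording completeness are not checked over the 3 days?

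*Combined protocol and SAP*

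**What the plan says.** Under Study Endpoints, the primary endpoint is "validity and reliability of portion size and energy intake measurement, measured with the PortionSize app in controlled and free-living conditions". The Phase 2 list in the Analysis section addresses free-living energy intake three times:

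- Objective 2, app against rater, covers energy and macronutrients as well as "food group estimation measured with the PortionSize app in free-living conditions is significantly different from the criterion value (rater analysis of individual food photos").
- Objective 3, app against requirements: "Determining if energy intake estimation measured with the PortionSize app in free-living conditions is significantly different from estimated energy requirements [8-10"].
- Objective 4, rater against requirements: "Determining if energy intake estimation measured from the rater analysis of food photos is significantly different from estimated energy requirements [8-10"].

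Objectives 1 and 2 call the rater analysis the criterion value. Objectives 3 and 4 do not use that term for requirements. No ranking or interpretation rule is given.

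On data capture, Procedures Involved (Phase 2) says that "participants will capture before and after pictures of the foods and food supplements they consume and use the app to quantify the portion sizes"; recording covers two weekdays and one weekend day. On weight stability, exclusion 4 is "Has gained or lost more than 10 lbs in last 3 months". The procedures table lists "Lifestyle and Demographics Questionnaire, RFPM Lifestyle Interview, Food Frequency Questionnaire, body weight, height, BMI" under Phase 1 only, and the return visit lists surveys. On completeness, the nearest texts are optional withdrawal for non-compliance (Withdrawal of Subjects) and weekly meetings that cover data integrity (Data Safety Monitoring Plan). Neither states a criterion.

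The Objectives section describes app feedback that steers users towards larger or smaller portions according to their weight goal. Potential Benefits to Subjects adds: "Participants may benefit by increased awareness of their portion sizes with various food groups". The plan does not say whether the feedback is switched on in Phase 2.

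**The concern.** Free-living energy intake is part of the primary endpoint, and objective 3 tests it in the same form of words as objective 2. A reader could take a significant objective 3 as a finding against the app, or a non-significant one as a finding for it. Either reading can be wrong. Unphotographed food lowers both the app and the rater estimate. People who photograph and size every portion may eat differently on those days. The requirement is itself an estimate. With no Phase 2 weight and no missed-meal or valid-day rule, these explanations cannot be told apart.

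The stake would be a mistaken conclusion on the primary endpoint: faulting an app that agrees with the rater, or passing one whose over-estimation happens to offset unrecorded food.

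**Working it through.** The plan gives no SD, significance level or effect size for these comparisons, so there is no stated figure to reproduce.

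**Inputs from the plan.** Up to 15 participants, 3 recording days, and the same participants and days for objectives 2, 3 and 4.

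**Assumed inputs.** Two-sided 5% level; one-sample and paired t-tests; normal errors; n=15. SDs in kcal/day for (intake minus requirement / app error / rater error): 500/200/100 as the central case, then 350/100/50, 350/200/100, 350/300/150, 550/100/50 and 550/300/150.

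**Step 1: how the three objectives are linked.** On the same participant-days,

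mean(app − requirement) = mean(app − rater) + mean(rater − requirement).

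The objective 3 gap is thus the objective 2 difference plus the objective 4 gap. Three tests carry two independent contrasts, and the part shared by app and rater is a single observed quantity with at least four possible sources. The inseparability is confirmed.

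**Step 2: what each comparison can see.**

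| Source of a gap | Objective 2 | Objectives 3 and 4 |
|---|---|---|
| Error in the app only | visible | visible in 3, not in 4 |
| Food not photographed | not visible | visible in both |
| Portion error common to app and rater | not visible | visible in both |
| Changed eating | not visible, and no bias | visible in both |
| Error in the requirement estimate | not visible, and no bias | visible in both |

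The second and third rows are errors in the free-living energy estimate that objective 2 cannot detect, because the rater works from the participant's own pictures. The linear identity therefore does not make objective 3 empty.

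**Step 3: smallest significant gap.** t(0.975, 14 df) × SD/√15:

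- SD 400: 2.145 × 400/√15 = 222 kcal/day
- SD 600: 2.145 × 600/√15 = 332 kcal/day

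**Step 4: simulation, 100,000 trials per scenario.** Central case, with the range over the six SD sets.

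| Scenario | Result | Central | Range |
|---|---|---|---|
| Shared gap 300, app unbiased against rater | objective 3 significant | 52.1% | 40.7-84.2% |
| Same | objective 2 significant | about 5% | 4.9-5.1% |
| Same | exactly one of 3 and 4 significant | 14.8% | 6.2-25.1% |
| No gap, no app bias | objective 4 not significant, given 3 significant | 41.1% | 20.0-70.0% |
| No gap, no app bias | 3 significant and 4 not, among all trials | 2.0% | 1.0-3.6% |
| App over-estimates by 200, shared shortfall of 200 | objective 2 significant and 3 not | 85.2% | 54.6-95.1% |

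**Step 5: reading the table.**

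- With a shared gap of 300, objectives 3 and 4 agree in 100 − 14.8 = 85.2% of trials (range 100 − 25.1 = 74.9% to 100 − 6.2 = 93.8%).
- In the central case both are significant in at least 52.1 − 14.8 = 37.3% of trials. At least 37.3/52.1 = 72% of significant objective 3 results therefore come with a significant objective 4, which shows that the gap is shared.
- The 41.1% is conditional on a 5% event: 0.411 × 5% ≈ 2% of trials.
- In the offsetting case exact cancellation was chosen, so objective 3 is non-significant about 95% of the time by construction. The criterion test, objective 2, usually finds the bias.

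**Step 6: how coarse the entry exclusion is.** Assuming 2500 to 3500 kcal per lb and 91 days, it admits a mean imbalance of up to 10 × 2500/91 = 275 to 10 × 3500/91 = 385 kcal/day. It also covers the months before entry rather than the 3 days. That confirms the control is weak. It does not bear on the app-versus-rater comparison.

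**The case for a change.** The best argument for a change is that it is cheap and the exposure real. Three sentences in Analysis and one in Procedures would state that app-specific error is judged from objective 2, that a gap shared by objectives 3 and 4 has no single cause, and whether feedback is active in Phase 2. Objective 4 reveals a shared gap but does not explain it, and comparing two significance verdicts is not a test of app against rater. The non-compliance clause and the weekly meetings are not completeness checks.

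All of that stands as description. Two things limit it. First, calling objectives 3 and 4 exploratory and not validity evidence goes too far. Requirements are the only Phase 2 reference not derived from the participants' pictures, so the label would discount the one comparison able to reveal under-recording or an error shared with the rater. Second, milder wording (supportive checks, shared gap not attributed) says what the plan's structure already conveys and what an analyst would write when reporting the results. Whether feedback is on is a missing detail; it affects how a shared gap is explained, not which analysis is run.

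**Conclusion.** No change to the plan. Energy balance and recording completeness are not specifically checked in Phase 2, and a gap common to app and rater cannot be attributed to one cause. But the plan claims no cause, keeps the term criterion value for the rater, contains the direct paired comparison, and pairs objective 3 with objective 4. The harm depends on a misreading that the plan does not invite. Keeping an ambiguous but photo-independent comparison in a pilot of up to 15 people is a fair trade-off. An end-of-Phase-2 weight would add little, since weight change over 3 days is a noisy measure of energy balance.

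The size is illustrative. At a shared gap of 300 kcal/day, objective 3 flags an app that is unbiased against the rater in about half of trials (41-84%), usually together with objective 4, while objective 2 holds its 5% level. With no gap and no bias, objective 3 stands alone as significant in about 2% of trials (1.0-3.6%). These figures rest on assumed SDs, gaps, normality and a 5% level. The contents of Appendix 2, the RFPM Lifestyle Interview and references 8-10 are not in the document. A completeness question in either instrument would narrow the ambiguity further.

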PBRC and LSU main campus has all the necessary equipment needed to undertake and execute the proposed research project successfully. All investigators and staff have offices or cubicles. Investigator offices are each equipped with a desk, chair, filing cabinets and shelves, telephone with voice mail, and access to a printer, photocopier and fax. Computers are equipped with software for statistics, data management, and word processing, and computers are connected to the PBRC mainframe with internet access and email access through Outlook Express. Information Technology (IT) provides full technical support to all members of the faculty and staff. PBRC has all the technological equipment and staff needed to conduct the present study. These information technologies assure efficient data handling and optimal communication among the investigators and the team.

Compensation

Participants will be compensated \$75 for successful completion of both Phase 1 and Phase 2. All compensation and recruitment success figures are based on historical averages from previous PBRC studies with similar respondent burden.

Confidentiality and Provisions to Protect the Privacy Interests of Subjects

Participants' records will be kept confidential to the extent allowed by law. Only Drs. [name], [name], and [name], and the PBRC research team will have access to the information participants provide. We will use an identification number rather than participants' names on study records. The information participants provide will be stored on secured network drives and will not be identified using any personal information.

Participants' names and other facts that might identify them will not appear when we present this study or publish its results. The findings will be summarized and reported in group form. Participants will not be identified personally. All participants will have ample opportunity during consent and throughout the study to ask questions concerning study procedures. These questions will be answered promptly and fully by study staff to ensure participant ease. A participant may choose not to answer questions or participate in study procedures at any time.

Data Safety Monitoring Plan

Study recruitment, study progress, participant complaints, data collection, data management, data integrity, data security, and eventually data analysis will be staffed at weekly meetings at PBRC.

Page 6 of 8 Version 3: 8/6/2020

Compensation for Research-Related Injury

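### Participants who struggle with the app in daily life could leave the study before the only free-living usability and satisfaction surveys; asking every Phase 2 starter remotely is a cheap improvement

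*Combined protocol and SAP*

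**What the plan says.** All references are to the combined protocol and SAP.

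- **Withdrawal of Subjects.** "Subjects may be withdrawn from the study if they are non-compliant with study procedures"; they are told by telephone or mail. No definition, threshold or timing of non-compliance is given. A separate paragraph allows voluntary withdrawal at any time and continues: "No additional data will be collected and they will be considered drop outs in the study".
- **Procedures Involved, Phase 2.** Participants photograph what they eat and estimate portions with the app for 3 days. They then return for the CSUQ and, last of all, the Phase 2 satisfaction survey. The procedures table lists these as paper surveys on return, and Study Timelines gives the same order.
- **Procedures Involved, Phase 1.** A preference survey and the CSUQ are completed at the laboratory visit, before any free-living use.
- **Study Endpoints.** Satisfaction and ease of use are secondary endpoints. Phase 2 objective 5 is "Quantifying satisfaction levels with the PortionSize app as measured in Appendix 2"; objective 6 is a qualitative account of the features users liked and disliked.
- **Number of Subjects.** "We expect up to 15 participants to complete both Phase 1 and Phase 2". Recruitment Methods sets the same figure, 15, as the most that will be recruited.
- **Setting.** Procedures may take place remotely by video call. This is not tied to the Phase 2 surveys.

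**The concern.** In most studies, failing to follow procedures and disliking the product are separate matters. Here they overlap. The main Phase 2 procedure is to use the app, so low use may itself be a sign that the app is awkward in daily life. The people best placed to say so are asked once, at the end and in person. The text gives no exit survey, no follow-up of people who do not return, no recording of reasons for loss, and no rule for missing survey responses.

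What is at stake is the free-living part of the secondary endpoints. If the people lost found the app harder than the others did, reported satisfaction and usability would look better than among everyone who tried the app at home. The list of disliked features would also be too short. That list may be the most useful product of a pilot whose stated purpose includes finding out whether the app is convenient and usable.

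**Working it through.** The plan states no dropout rate, no target for the surveys and no precision figure, so there is no figure to reproduce. The check has two parts: the order of events, and the scale of what a lost survey leaves open.

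**1. Order of events**

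| Step | Source | Can a person be lost here? |
|---|---|---|
| Phase 1 laboratory visit, preference survey, CSUQ | Procedures Involved, Phase 1 | Any later loss leaves these answers in hand |
| 3 days of free-living app use | Procedures Involved, Phase 2 | Yes: staff withdrawal, voluntary withdrawal |
| Return visit | Study Timelines; procedures table | Yes: by not attending |
| Phase 2 CSUQ, then satisfaction survey | Procedures Involved, end of Phase 2 | These are the only free-living surveys |

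Each way of leaving comes before the Phase 2 surveys, and the text gives no other way to obtain them. The gap therefore exists in the plan as written. Whether anyone falls into it is not known.

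**2. Scale**

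Inputs:
- n = number starting Phase 2. At most 15 can start, because at most 15 are recruited (Recruitment Methods). Phase 2 is described as involving the 15 people from Phase 1.
- k = starters without Phase 2 surveys. This is an assumption; the documents give nothing to set it.
- m = mean result among those surveyed, and x = unknown mean among the k not surveyed, both rescaled to run from 0 to 1.

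Mean over all starters = [(n − k)·m + k·x] / n.

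The best case is x = 1 and the worst is x = 0. The difference between them is k/n, whatever m is. With n = 15:

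- k = 1: 1/15 = 6.7 points on a 0-100 scale
- k = 2: 2/15 = 13.3 points
- k = 3: 3/15 = 20.0 points

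Fifteen is a ceiling, so fewer starters would widen the range. For example, an assumed n = 12 with k = 1 gives 1/12 = 8.3 points.

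**3. Direction**

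Surveyed mean minus all-starter mean = m − [(n − k)·m + k·x]/n = (k/n)·(m − x).

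This is positive, meaning the report is too favourable, only if x < m. The documents do not say that people who use the app little or fail to return are less satisfied. That is a reasonable inference and no more. The range in step 2 is a limit on what missing surveys leave unknown, for any cause of loss. It is not an estimate of bias.

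**The case against.** The strongest reply is that the harm is conjecture. By the withdrawal route, someone must use the app little, staff must choose to apply a discretionary rule for that reason, they must do so before the return visit, and the person must be less satisfied than the rest. The text states none of these. Use lasts only 3 days, and no monitoring during those days is described. All of this stands, which is why the point is worded as a possibility. It does not close the gap, because simply not returning leads to the same place without the rule being used. Non-return is a feature of any study with a return visit, but here it bears directly on what is being measured.

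Second, Phase 1 already collects satisfaction, ease of use and opinions on features. This also stands, and it limits the reach of the point. Those answers come before free-living use, however, and cannot report on it. The weekly staff meetings that review complaints are no substitute for a survey.

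Third, consent pages and the appendices are not in the text available, and further arrangements could appear there. The point is confined to the text at hand.

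A reader might infer more than the documents support:

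- *That low users will be withdrawn.* The rule is permissive, and nothing says low use counts as non-compliance.
- *That withdrawn people may not be surveyed.* The sentence ending data collection follows voluntary withdrawal, in a separate paragraph from staff withdrawal. Its reach to staff withdrawal is unclear, so it cannot be read as a bar.
- *That payment drives low users away.* Payment is "for successful completion of both Phase 1 and Phase 2". This could discourage someone who doubts they qualify, or give them a reason to return.
- *That 15 is the number of completers, with more starting.* The Number of Subjects sentence alone could be read so, but Recruitment Methods caps recruitment at 15.
- *That keeping low users requires a restricted analysis of the comparisons with energy requirements (Phase 2 objectives 3 and 4).* The plan does not say that data from withdrawn people are excluded, and a meal that was never photographed leaves no trace by which to judge complete capture.

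**Conclusion.** The concern holds as a minor one. The plan leaves a route by which people who struggled with the app at home could go unasked, and it offers no second chance to ask them. The effect is confined to Phase 2 objectives 5 and 6 and the free-living CSUQ. Phase 1 survey results do not depend on it.

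The likely number lost cannot be determined from the documents. A favourable lean requires those lost to be less satisfied than those surveyed, which is inferred. These results are descriptive, and no cut-off or decision hangs on them. The reason to act is that, with so few people, each missing survey matters and the remedy costs little. This is a cheap improvement, not a flaw that undermines the pilot.

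**What to change.** 1. State in Withdrawal of Subjects that low app use in Phase 2 is not by itself a reason for withdrawal before the Phase 2 surveys.
2. Offer the Phase 2 CSUQ and satisfaction survey by mail, telephone or video to every Phase 2 starter who does not return or is withdrawn by staff, except those who have asked to leave. Anyone may decline, consistent with the existing assurance: "A participant may choose not to answer questions or participate in study procedures at any time". The plan already uses telephone, mail and video contact, so no new channel is needed.
3. Report survey results with the number of Phase 2 starters as denominator, days of app use out of 3, and the number without surveys by reason (staff withdrawal, voluntary withdrawal, not returned). It is enough to show days of use alongside the intake results; no further intake analysis is needed for this point.

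**Cost.** Some protocol wording and a few extra contacts. Survey modes would be mixed, so the mode should be recorded and reported. Usability figures may come out less favourable.
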